| | 
• Airway Clearance Satisfaction surveys will be conducted. Results from the active treatment period will be compared to the baseline period, during which the subject received his/her regular airway clearance regimen.Any device related adverse events which occur after initial therapy with The Volara® System will be recorded.Any equipment related complaints which occur after initial therapy with The Volara® System will be recorded. |
| Subject Withdrawal: | Subjects may withdraw consent to participate in the study at any time. The subject may also be withdrawn from the study according to investigator judgement regarding the continued health or safety of the subject or related to inability or unwillingness to perform study therapy or procedures. Removal of subjects may occur for any of the following reasons: 
• Subject enrolled in violation of inclusion/exclusion criteria• Inability to tolerate OLE therapy• Adverse event or adverse device effect that occurs during therapy• Physician judgement that the patient is not a good candidate for the study• Inability or unwillingness to perform OLE therapy and data collection maneuvers as directed |
| Statistical Methods: | Descriptive summary statistics will be provided for demographics, the primary and secondary endpoints. Continuous data will be summarized with N, mean, median, standard deviation, min, and max. Categorical data will be summarized with the number and percent of patients in each category. Incidence of adverse device effects (ADEs) will be tabulated. |

PROTOCOL TITLE

Evaluation of Oscillation and Lung Expansion (OLE) using The Volara® System for treatment of respiratory complications in patients with neuromuscular disease in the home setting

Final Protocol

Protocol Number: CR-RR-2020-005

Date: 11May2022

| | |
|--|---|
| | Incidence of device-related complaints will be tabulated. |
|--|---|

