3.3.3.5 Home Training on The Volara® System: A Hillrom designated trainer will set up the device and review operation and treatment protocol at the time the device is delivered. Study subjects and caregivers will be instructed to use the device as their primary airway clearance and lung expansion therapy for a period of six months. Hillrom training staff will follow up with each Volara user according to the standard device placement and follow-up program.

3.3.3.6 Adherence Documentation: During the six-month follow-up period, adherence to the daily prescribed therapy regimen will be assessed. The Volara® System logs therapy details for each therapy completed, including the total time of therapy, the number of stages completed, the total time in CPEP mode, total time in CHFO mode and peak pressures achieved in each mode. Adherence data logs will be downloaded on a regular basis during the active treatment period.

3.3.3.8 One-month Virtual Study Visit: A one-month study visit with each study subject will be conducted virtually. Visits will be completed +/- 3 days from the one-month scheduled visit date. During this visit, the following procedures and assessments will be conducted:

- Review of study procedures with subject/caregiver
- Review of current respiratory status, respiratory treatments, and medications
- Documentation of patient/caregiver reported exacerbations and medical interventions for the prior period (run-in and first month of Volara therapy)
- Documentation of any Adverse Device Effects that the subject experienced during the follow-up period
- Completion of QOL questionnaire
- Completion of Patient/Caregiver Satisfaction survey

3.3.3.9 Three-month and Six-month Virtual Study Visits: Three-month and six-month study visits with each study subject will be conducted virtually by study staff. Visits will be completed

PROTOCOL TITLE

Evaluation of Oscillation and Lung Expansion (OLE) using The Volara® System for treatment of respiratory complications in patients with neuromuscular disease in the home setting

Final Protocol

Protocol Number: CR-RR-2020-005**Date:** 11May2022

+/- 3 days from the one-month scheduled visit date. During these visits, the following procedures and assessments will be conducted:

- Review of study procedures with subject/caregiver
- Review of current respiratory status, respiratory treatments, and medications

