4. ICU LOS
5. Number of Outpatient Visits
6. Antibiotic Use Days
7. Pulmonary Function Testing
 - SVC
 - PCF
 - Resting SpO₂
 - MIP
8. QOL Assessment
9. Adherence to OLE Therapy Regimen
10. Patient/Caregiver Satisfaction

Comparison of Pre-treatment and Active Treatment Periods

Rate of exacerbation and health care utilization will be evaluated to compare the active treatment period and the control periods (six-month period immediately prior to active treatment and six-month seasonally equivalent time-period). Remaining endpoints will compare baseline assessments to assessments obtained during the active treatment period. Comparisons will be conducted for the purpose of identifying any statistical associations that can be attributed to use of OLE treatment with The Volara® System.

General Study Information**4.1 Technical Support for Device(s)**

Technical support will be performed by Hillrom following routine service practices (contact details will be provided).

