5.0 Safety and Device Complaint Definitions and Reporting Requirements

Safety surveillance within this study and the safety reporting both performed by the investigator, starts as soon as the subject signs informed consent (and assent if minor subject) and receives the first study-specific treatment. The safety surveillance and the safety reporting will continue until the last study-specific test has been performed, the subject/investigator concludes his participation into the study or the subject/investigator withdraws the subject from the study, except as otherwise specified in the protocol.

Reportable events:

- (1) Adverse Device Effects (adverse event related to the device) associated with the use of The Volara® System
- (2) Device Complaints associated with The Volara® System

During the study, safety events and device complaints must be reported to the Sponsor within 24 hours of becoming aware of the event. Please contact [REDACTED] by phone: [REDACTED] or email: [REDACTED].

PROTOCOL TITLE

Evaluation of Oscillation and Lung Expansion (OLE) using The Volara® System for treatment of respiratory complications in patients with neuromuscular disease in the home setting

Final Protocol

Protocol Number: CR-RR-2020-005

Date: 11May2022

A complaint is defined as any written, electronic or oral communication that alleges deficiencies related to the identity, quality, durability, reliability, safety, effectiveness, or performance of the device after its release for distribution (21 CFR 820.3(b)).

Any device Complaint and/or reported safety event be reviewed, evaluated, and investigated by Hillrom and reported to the appropriate Health Authority per current regulations.

Additional information may be requested, when required, by the Sponsor in order to support the reporting of safety events to regulatory authorities.

The investigator must notify the IRB/EC, if appropriate, in accordance with national and local laws and regulations, of the safety and/or complaint events reported to the Sponsor.

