5.5.1 Unanticipated Serious Adverse Device Effect (USADE) Definition

A serious adverse device effect which by its nature, incidence, severity or outcome has not been identified in the current version of the risk analysis report.

1. UADE [applicable to investigational studies following FDA regulations]

As defined in 21 CFR §812.3, unanticipated adverse device effects (UADE) are defined as any serious adverse effect on health or safety or any life-threatening problem or death caused by, or associated with, a device, if that effect, problem, or death was not previously identified in nature, severity, or degree of incidence in the clinical investigational plan or application (including a supplementary plan or application), or any other unanticipated serious problem associated with a device that relates to the rights, safety, or welfare of subjects.

If an unanticipated adverse device effect occurs, the investigator must notify Hillrom and the IRB/EC immediately, but no later than 10 working days of the investigator's knowledge of the event, as required by 21 CFR §812.150. Hillrom will take any steps necessary to investigate the event and will be responsible for notifying FDA and all other participating IRBs/ECs and investigators.

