5.6 Subject Death

All subject deaths are to be documented and reported to the sponsor within 72 hours after becoming aware of the event.

PROTOCOL TITLE**Evaluation of Oscillation and Lung Expansion (OLE) using The Volara® System for treatment of respiratory complications in patients with neuromuscular disease in the home setting**

Final Protocol

Protocol Number: CR-RR-2020-005**Date:** 11May2022**5.7 Complaint or Device Deficiency Definition**

A complaint is defined as any written, electronic or oral communication that alleges deficiencies related to the identity, quality, durability, reliability, safety, effectiveness, or performance of the device after its release for distribution (21 CFR 820.3(b)).

Any device complaint and/or allegation of injury shall be reviewed, evaluated, and investigated by Hillrom Post Market Surveillance and reported to the appropriate Health Authority per current regulations. The Investigators are responsible for informing the Institutional Review Boards, as per their guidelines.

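### No written route carries adverse device effects or complaints heard by sponsor trainers and technical support into the study data, and the SAP has no table for the promised complaint incidence

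*Protocol*

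**What the plan says.** **Who reports.** Protocol section 5.0 states: "Safety surveillance within this study and the safety reporting both performed by the investigator". Reports run towards the sponsor: "safety events and device complaints must be reported to the Sponsor within 24 hours of becoming aware of the event". Section 6.1 likewise has serious and unanticipated adverse device effects going to the sponsor and to the IRB/EC under local policy.

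**Who meets the subject about the device.** Under section 3.3.3.5, "A Hillrom designated trainer will set up the device and review operation and treatment protocol at the time the device is delivered", and afterwards "Hillrom training staff will follow up with each Volara user according to the standard device placement and follow-up program". Section 4.1 adds: "Technical support will be performed by Hillrom following routine service practices".

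**What happens to complaints.** Section 5.7 says that a complaint or alleged injury "shall be reviewed, evaluated, and investigated by Hillrom Post Market Surveillance and reported to the appropriate Health Authority per current regulations". Section 5.0 contains a similar provision. Both define a complaint broadly enough to include something said aloud.

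**What is promised.** The Synopsis (Methods) says that device-related adverse events and equipment complaints arising after the first treatment will be recorded, without limiting this by who was told. Its Statistical Methods entry promises adverse device effect incidence and adds: "Incidence of device-related complaints will be tabulated".

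**What the SAP plans.** Section 2.5 and Appendix 1 provide adverse event tables, including tables by relationship to the device. No table or listing covers complaints. Section 3, on changes from the protocol, mentions only that adherence will not be analysed.

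**The concern.** This is a decentralised home study: visits are in the home or virtual, and the people most closely involved with the device are the sponsor's. A subject with a fault, a leak or an unpleasant effect during treatment may well mention it to the trainer or the support line. If the matter goes no further than the sponsor's commercial complaint system, the sponsor holds the information, the treating investigator does not, and the study table omits it.

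Protocol sections 1.1 and 1.2 say that data on effectiveness in the home are limited and that this device has had no formal clinical study. An incomplete count of device effects would be falsely reassuring about the very setting the study is meant to inform, and the missing reports would already be in the sponsor's files.

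**Working it through.** The documents give no adverse device effect rate, no complaint rate and no share of reports expected to reach the sponsor first. There is no figure to reproduce, so the check follows an event through the text.

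1. **Subject to sponsor staff.** The channel exists. Sections 3.3.3.5 and 4.1 put the sponsor's trainer, follow-up staff and technical support in contact with subjects, under the sponsor's standard placement programme and routine service practice and not under a study procedure.

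2. **Sponsor staff to site.** I looked for a step in sections 3.3.3.5, 4.1, 5.0, 5.7, 6.1 and 6.2 and found no general one. The single stated route outward from the sponsor is in section 5.5.1, where the sponsor "will be responsible for notifying FDA and all other participating IRBs/ECs and investigators". It applies to unanticipated adverse device effects only. Because it follows a sentence requiring the investigator to notify the sponsor, it reads as presuming that the treating investigator reported first.

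3. **Sponsor file to study database.** Sections 5.0 and 5.7 send complaints to the sponsor's own evaluation and to the health authority. Neither mentions the case report form, and no reconciliation before lock is described in either document.

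4. **Could the site recover the event by asking?**

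| Contact | Adverse device effect item listed? |
|---|---|
| 1-month visit (3.3.3.8) | Yes |
| 3- and 6-month visits (3.3.3.9) | No |
| Monthly pulmonary function visits (3.3.3.10) | No, four measurements only |
| Table 1 | Row for each occurrence, not tied to a visit; no complaint row |

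After month 1 no visit list prompts the question. Table 1 tells the site to record the effects it knows of; it does not tell sponsor staff to pass any on.

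5. **Study database to table.** For adverse device effects a table exists (SAP 2.5.1.2 and Appendix 1), so anything lost at steps 2 to 4 lowers its count. For complaints there is no table or listing to lower. The Synopsis promise lapses whoever receives the complaint, and SAP section 3 does not say so.

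**The case against.** The best answer is that the Synopsis already requires recording of all such events and complaints without regard to who heard them, and Table 1 captures adverse device effects at each occurrence. On that reading the plan, followed faithfully, includes what the sponsor hears. The 24-hour duty in section 5.0 is in the passive and could be read as binding sponsor staff too. Section 6.2 commits the sponsor to written operating procedures, and section 6.1 requires those assisting with the study to be informed of their duties, so forwarding and reconciliation may be set out in documents not available here. The contact for the 24-hour reports is blacked out, so it cannot be told whether site reports and user complaints reach the same intake. A subject who tells a trainer can also tell study staff.

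Much of this stands, and it rules out three stronger readings that a reader might infer.

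- That the investigator is the *sole* permitted reporter. Section 5.0 names no one else, but it does not exclude others.
- That events told to the sponsor *necessarily* stay out of the tables. No section says so, and the Synopsis points the other way. This is a risk arising from a missing procedure.
- That the investigator is made answerable to the IRB/EC for events known only to the sponsor. Section 5.0 qualifies that duty as applying where appropriate, and in context it most naturally concerns events the investigator has reported.

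What the objection does not supply is the mechanism. A promise to record everything is not a route, and a 24-hour duty that ends at the sponsor does not bring a report back to the site.

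**Conclusion.** The gap is real and should be closed. The protocol promises complete recording but writes no path from the sponsor's trainers, technical support or post-market surveillance to the site or the study database, and after month 1 it lists no visit enquiry that would compensate. The direction of any error in the adverse device effect count from this cause is downward. Its size cannot be estimated from the documents.

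A reader might be tempted to attach a number. With no recorded event in 70 treated patients, the one-sided 95% upper limit is 1 − 0.05^(1/70) = 4.19%. If 25% or 50% of events were missed, the supportable limit would become 4.19%/0.75 = 5.59% or 4.19%/0.50 = 8.38%. The arithmetic is sound but only rescales an assumed share for which the documents give no basis. It also treats the approximate enrolment of 70 as the number treated. It shows sensitivity and is not an estimate of the under-count.

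The complaint point rests on no such assumption: the Synopsis promises an incidence, the SAP plans none, and the change is undeclared.

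The conclusion on adverse device effects assumes that no unseen operating procedure or study agreement already provides for forwarding and reconciliation. If one does, the remedy for that part reduces to citing it.

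**What to change.** - In Protocol sections 3.3.3.5, 4.1 and 5.0, require sponsor training and technical-support staff to forward any adverse device effect or complaint received from a study subject to the site, for entry on the study form, within a stated limit such as 24 hours. This is a new duty, since the existing limit runs only to the sponsor.
- Before database lock, reconcile the sponsor's complaint file for study devices with the study database, and base the counts on the reconciled set. Section 6.2 already has the sponsor keep device shipment and disposition records. Because section 4.2 de-identifies subjects by code, matching would use the device identifier and the subject code.
- Add adverse device effect enquiry to the 3- and 6-month visit lists in section 3.3.3.9.
- Add a complaint table to the SAP, or state in SAP section 3 that complaint incidence will not be tabulated.

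No visit is added. The cost is protocol and SAP wording, a linkage arrangement, one reconciliation step and some staff time for forwarding. Reported incidence may be higher as a result. If follow-up has already ended, the reconciliation can still be done before lock or reporting.

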5.1 Foreseeable Risks and Benefits of the Clinical Study

5.1.1 Anticipated risks associated with study participation include, but are not limited to:

- Hyperventilation
- Decreased cardiac output
- Headache
- Increased air trapping
- Pulmonary air leak
- Pneumothorax
- Pulmonary hemorrhage

There may be other risks or discomforts associated with receiving this therapy which are currently unforeseen.

PROTOCOL TITLE

Evaluation of Oscillation and Lung Expansion (OLE) using The Volara® System for treatment of respiratory complications in patients with neuromuscular disease in the home setting

Final Protocol

Protocol Number: CR-RR-2020-005

Date: 11May2022

5.1.2 Possible benefits of study participation include, but are not limited to:

- Information learned about use of OLE therapy in patients with NMD in this study may help doctors learn more about treating patients with the same condition in the future.
- Study participation may contribute to improving the health of patients with NMD.
- It is possible that there will be no benefit from study participation.

5.2 Adverse Event (AE) Definition

Any untoward medical occurrence, unintended disease or injury, or untoward clinical signs (including abnormal laboratory findings) in subjects, users or other persons, whether or not related to the investigational medical device under study.

This definition includes events related to the investigational medical device.

This definition includes events related to the procedures involved.

5.3 Serious Adverse Event (SAE) Definition

An adverse event that led to:

- Death
- A serious deterioration in the health of the subject, that either resulted in:
 - A life-threatening illness or injury OR

PROTOCOL TITLE**Evaluation of Oscillation and Lung Expansion (OLE) using The Volara® System for treatment of respiratory complications in patients with neuromuscular disease in the home setting**

Final Protocol

Protocol Number: CR-RR-2020-005**Date:** 11May2022

- A permanent impairment to a body structure or a body function OR
- An in-patient or prolonged hospitalization OR
- A medical or surgical intervention to prevent life-threatening illness or injury or permanent impairment to a body structure or a body OR
- A malignant tumor
- Fetal distress, fetal death or a congenital abnormality or birth defect
- A planned hospitalization for a pre-existing condition, or a procedure required by the protocol is not considered a serious adverse event.

5.4 Adverse Device Effect (ADE) Definition

An adverse event related to the use of an investigational medical device.

This definition includes adverse events resulting from insufficient or inadequate instructions for use, deployment, implantation, installation, or operation, or any malfunction of the investigational medical device.

This definition includes any event resulting from the use error or from intentional misuse of the investigational medical device.

5.5 Serious Adverse Device Effect (SADE) Definition

Adverse device effect that has resulted in any of the consequences characteristic of a serious adverse event.

PROTOCOL TITLE

Evaluation of Oscillation and Lung Expansion (OLE) using The Volara® System for treatment of respiratory complications in patients with neuromuscular disease in the home setting

Final Protocol

Protocol Number: CR-RR-2020-005

Date: 11May2022

5.5.1 Unanticipated Serious Adverse Device Effect (USADE) Definition

A serious adverse device effect which by its nature, incidence, severity or outcome has not been identified in the current version of the risk analysis report.

1. UADE [applicable to investigational studies following FDA regulations]

As defined in 21 CFR §812.3, unanticipated adverse device effects (UADE) are defined as any serious adverse effect on health or safety or any life-threatening problem or death caused by, or associated with, a device, if that effect, problem, or death was not previously identified in nature, severity, or degree of incidence in the clinical investigational plan or application (including a supplementary plan or application), or any other unanticipated serious problem associated with a device that relates to the rights, safety, or welfare of subjects.

If an unanticipated adverse device effect occurs, the investigator must notify Hillrom and the IRB/EC immediately, but no later than 10 working days of the investigator's knowledge of the event, as required by 21 CFR §812.150. Hillrom will take any steps necessary to investigate the event and will be responsible for notifying FDA and all other participating IRBs/ECs and investigators.

5.5.2 Anticipated Serious Adverse Device Effect (ASADE) Definition

A serious adverse device effect which by its nature, incidence, severity or outcome has been previously identified in the risk analysis report.

5.6 Subject Death

All subject deaths are to be documented and reported to the sponsor within 72 hours after becoming aware of the event.

PROTOCOL TITLE**Evaluation of Oscillation and Lung Expansion (OLE) using The Volara® System for treatment of respiratory complications in patients with neuromuscular disease in the home setting**

Final Protocol

Protocol Number: CR-RR-2020-005**Date:** 11May2022**5.7 Complaint or Device Deficiency Definition**

A complaint is defined as any written, electronic or oral communication that alleges deficiencies related to the identity, quality, durability, reliability, safety, effectiveness, or performance of the device after its release for distribution (21 CFR 820.3(b)).

Any device complaint and/or allegation of injury shall be reviewed, evaluated, and investigated by Hillrom Post Market Surveillance and reported to the appropriate Health Authority per current regulations. The Investigators are responsible for informing the Institutional Review Boards, as per their guidelines.

